#### 6.2.3.11. *Current Medications (Appendix 16)*

In order to assess the potential impact of medication use concurrent with study participation, we will ask study participants about their use of prescription psychotropics (including stimulants,

anxiolytics, and depressants), anticonvulsants, anticholinergic drugs, and sympathomimetics/sympatholytics. Given that the mechanism of action of SGB is unknown but likely involves some combination of central, peripheral, and autonomic pathways, use of these medications could be confounding. These data will be collected to support secondary objective 2.

#### 6.2.3.12. Other Questions (*Appendix 17*)

Additional questions will be asked at week 0 that are not part of an established, standardized assessment. In order to determine whether duration of PTSD symptoms moderate any treatment effects that may be seen in our study, we will ask study participants whether they have been diagnosed with posttraumatic stress (PTS) or posttraumatic stress disorder (PTSD), and if so, the month and year when they received this diagnosis. For those who indicate that they have not been diagnosed, we will ask for the approximate month and year when their symptoms started.

Similarly, because nicotine has a direct impact on the sympathetic nervous system, we will ask study participants four items that will allow for calculation of estimated pack years for cigarette smoking. These items will establish age at initiation of regular smoking, smoking longevity (whether they have smoked at least 100 cigarettes in their lifetime), recency of regular smoking, and number of cigarettes typically smoked. The resulting pack-year estimate will be assessed for any moderation of treatment effects among study participants. A similar estimate will be computed for chewing tobacco, snuff, or other smokeless tobacco exposure.

### 6.3. Treatment and Treatment Assessments (Weeks 0 and 2)

The PCL-5, PCL-C, K6, and the M.I.N.I.-Plus Suicidality Items will be administered prior to the procedure at week 2.

Standard right-sided SGBs will be performed in accordance with this protocol ([Section 3.1](#)). On the day of the procedure, clinic nursing staff will perform standard nursing intake to include brief interim history, review of systems, vital signs, and placement of intravenous catheter. Females of child-bearing potential will have a urine pregnancy test. The treating physician will perform a targeted history and physical, paying attention to potential contraindications to SGB. At week 0, the physician will also give a brief explanation of the procedure as well as a review of risks and potential benefits, though these will have been described to them beforehand.

Injections will be performed under ultrasound visualization. The study medication will be either 7-10 mL 0.5% ropivacaine injected ventral to the right longus coli muscle (around and into the ventral fascia) and into the longus coli immediately dorsal to the presumed ventral fascia, at the level of the C6 anterior tubercle (landmarks for the stellate ganglion; active study medication) or 1-2 mL preservative free normal saline injected anterolateral to the anterior tubercle of C6 (sham procedure). The treating physician will access participant assignment (performed at RTI per protocol) via email from RTI's central office. The participant will not be informed which treatment he or she is receiving; for blinding purposes, the same type of syringes will be used for both injections. Similarly, the same number and types of syringes and other supplies should be placed on the sterile procedure table regardless to which intervention (SGB or sham) the participant has been randomized. The interaction of the treating physician with the participant will be scripted as much as possible (**Appendix 18**). Customary vital signs will be recorded. MEDCOM 40-54 dated Feb 09 provides "a standard process and procedure for

surgical and procedural site verification of patients undergoing operative or other invasive procedures”. In accordance with this regulation, the participant’s identity, the procedure to be performed, and the specific site of the procedure will be verified. A separate paper CRF will be created for the procedure; this information will not be shared with anyone outside the treatment suite (RC, participant, other members of the RTI Project Team, etc.). It is critical that only the physician administering the treatment (and his immediate team) be aware of the participant’s assignment to active or sham intervention. Following the intervention, the treating physician should have no further contact with the participant except as required for participant safety.

Immediately following each SGB procedure, the subject will be observed in the procedure suite prior to transport to the recovery area for assessment of potential complications that could require immediate intervention, according to local clinic policy. The participant then will be taken to the post-procedure recovery area, where monitoring of vital signs will continue under the supervision of the recovery nurse for 20 minutes or longer, again per local clinic policy and participant condition.

The RC will assess the participant at 30 minutes post-procedure for his/her Horner’s syndrome, recording the time post-SGB and using the following metrics (0 for absent, 1 for slight, 2 for obvious) when the participant is sitting up straight and not facing a bright light:

- ptosis
- scleral injection
- miosis

Assuming the absence of complications requiring further evaluation or treatment, the participant will be given discharge instructions, and will be required to verbally indicate understanding of signs and symptoms that would require emergency care (e.g., shortness of breath or difficulty breathing, increasing neck pain). In addition, the clinic nurse will remind the participant that soreness at the injection site, a full sensation of the throat, and Horner’s symptomology may occur for 6-18 hours (the duration of effect of the local anesthetic); if the recurrent laryngeal nerve has been blocked, there may also be hoarseness and difficulty swallowing. The participant then will be allowed to leave the clinic per local site policy.

#### **6.4. Post-Treatment Assessments (Weeks 4, 6, and 8)**

With the exception of the final CAPS-5, it is expected that these instruments will be completed by the participants on their own devices using a secure Web-based platform. For analytical purposes, each follow-up period will begin 2 days before the exact date of the follow-up and will end 11 days after the exact date of the follow-up. For example, the 2-week follow-up period will begin on day 12 and will end on day 25, the 4-week follow-up period will begin on day 26 and will end on day 38, etc. See **Appendix 19-1** and **19-2** for email communications, phone reminder script and contacting schedule.

##### **6.4.1. CAPS-5**

The CAPS-5 will be repeated, again via phone interview, at approximately 8 weeks following the first SGB, in support of the primary objective.

##### **6.4.2. PCL-5**

The PCL-5 will be repeated at weeks 4, 6, and 8 in support of secondary objective 1.

#### **6.4.3. PCL-C**

The PCL-C will be repeated at weeks 4, 6, and 8 in support of secondary objective 1.

#### **6.4.4. M.I.N.I.-Plus Suicidality Items**

The M.I.N.I.-Plus Suicidality Items will be repeated at weeks 4, 6, and 8, and is intended to enhance participant safety and support secondary objective 3. In most cases these assessments will take place via a secure web portal on the participant's device of choice (i.e., there will be no interaction between the participant and the RC at these times). If an individual affirmatively on any of the first seven M.I.N.I.-Plus items regarding suicidal ideation in the previous 2 months, they will be asked an additional 4 questions regarding *current* suicidal ideation or plans. If a participant answers affirmatively to currently wanting to harm themselves, thinking about committing suicide, having a plan, or planning to act on a plan, an automated participant safety system will be triggered (see [Section 6.4.13](#)).

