### Criteria for Evaluation:

Safety:	adverse events
----------------	----------------

Efficacy:	A 10 point decrease in mean CAPS-5 scores pre-treatment (prior to week 0) to 8 weeks post-treatment
------------------	---

Acceptability:	service members' and providers' decision-making processes and information needs related to stellate ganglion block
-----------------------	--

---

Statistical Methods:	Estimates of CAPS-5 total symptom score change between week 8 and pre-week 0 will be compared between the two treatment arms (active and sham) using a linear model that also accounts for study site, the initial (prior to week 0) CAPS-5 score, as well as potential confounding variables (e.g., concomitant medications, duration of PTSD, post-block Horner's syndrome, etc.) depending on availability. Output from the model will include adjusted point estimates of the average 8-week change in CAPS-5 symptom score for each treatment arm, the estimated average difference in the change between the two treatment arms, and corresponding 95% confidence intervals for each of these estimates, as well as a formal test of hypothesis of the difference in the scores between the two treatment arms.
-----------------------------	---

We will analyze the effect of SGB on clinical criteria of PTSD as measured by the PCL-5 over time. We will assess differential treatment effects at weeks 2, 4, 6, and 8. The outcome variable in each model will be the binary outcome of diagnosis and the models will account for arm classification, week and study site; two-way and three-way interactions of treatment will also be included in the model.

Other secondary outcomes similarly will be assessed using linear mixed models or generalized models, as appropriate for the structure of the outcome measure.

---

All essential documents are being archived as required  
by the study contractual agreements or protocol.

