## 7. ADVERSE EVENTS AND DEVIATION MANAGEMENT

### 7.1. Research Monitor

This trial is not a safety study; SGB is a well-studied procedure with a low probability of serious adverse events (Wulf & Maier, 1992), and a smaller volume of saline injected superficially to the region of the SG would be expected to result in even fewer serious adverse events. Nevertheless, reports of adverse events will be collected during the trial, and the Research Monitor is required to review all unanticipated problems involving risk to volunteers or others, Serious Adverse Events (SAE) and all volunteer deaths associated with the protocol and provide an unbiased written report of the event. At a minimum the Research Monitor should comment on the outcomes of the event or problem and in the case of a SAE or death comment on the relationship to participation in the study. The Research Monitor should also indicate whether he/she concurs with the details of the report provided by the Study Investigator. All unanticipated problems involving risk to subjects or others will be promptly reported to the USAMRMC Office of Research Protection (ORP) Human Research Protection Office (HRPO) by [contact]), by email ([[contact]](mailto:[contact])), or by [contact]) or mail to the US Army Medical Research and Materiel Command, ATTN: MCMR-RP, [name].

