### 7.2. Adverse Events

An adverse event (AE) is any untoward medical occurrence in a clinical investigation participant administered a medicinal product and which does not necessarily have a causal relationship with this treatment. An AE can therefore be any unfavorable and unintended sign, symptom, or disease temporally associated with the use of a medicinal product, whether or not considered related to the medicinal product. AEs may also include pre- or post-treatment complications that occur as a result of protocol-mandated procedures (e.g. invasive procedures such as venipuncture, biopsy, etc.). Pre-existing events which increase in severity or change in nature during or as a consequence of use of a medicinal product in human clinical trials will also be considered AEs.

Any reported medical condition or clinically significant laboratory abnormality with an onset date before the screening visit and not related to study procedures is considered to be pre-existing, and should be documented in the case report form.

Any AE (i.e., a new event or an exacerbation of a pre-existing condition) with an onset date after the screening visit up to the last day on study (including the follow-up, off study medication period of the study), should be recorded as an AE on the appropriate CRF page(s).

An AE does not include:

- Medical or surgical procedures (e.g. surgery, endoscopy, tooth extraction, transfusion); the condition that leads to the procedure is an adverse event.
- Pre-existing diseases or conditions or laboratory abnormalities present or detected prior to the screening visit that do not worsen.
- Situations where an untoward medical occurrence has not occurred (e.g. hospitalization for elective surgery, social and/or convenience admissions).
- Overdose of either study drug or concomitant medication without any signs or symptoms unless the participant is hospitalized for observation.

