## **7.6. Serious Adverse Event Reporting Requirements**

### **7.6.1. All Serious Adverse Events**

RTI International, the Research Monitor, and HRPO must be notified immediately regarding the occurrence of any unanticipated and/or serious adverse event that occurs after the screening visit, including serious adverse events resulting from study procedures performed from screening onwards. The procedures for reporting all serious adverse events, regardless of causal relationship, are as follows:

- Record the unanticipated and/or SAE on the AE CRF and complete the “Serious Adverse Event Report” form.
  - Fax and email the serious adverse event report to the attention of RTI International and HRPO within 24 hours of the investigator’s knowledge of the event. Contact information is below.
  - For fatal or life-threatening events, also fax and email copies of hospital case reports, autopsy reports, and other documents when requested and applicable.

RTI International Principal Investigator: Name: [name] [name]  
Title Chief Medical Officer  
[contact]  
Mobile [contact]  
Email: [[contact]](mailto:[contact])

RTI International Co-Investigator: Name: [name]  
[contact]  
Mobile [contact]  
[contact]  
Email: [[contact]](mailto:[contact])

HRPO: [contact]  
[contact]  
Email: [[contact]](mailto:[contact])

Research Monitor: Name: MAJ [name] MD  
[contact]  
[contact]  
[contact]  
Email : [[contact]](mailto:[contact])

RTI International may request additional information from the Investigator to ensure the timely completion of accurate safety reports.

The Investigator must take all therapeutic measures necessary for resolution of the SAE. Any medications necessary for treatment of the SAE must be recorded onto the concomitant medication section of the participant's CRF.

Follow-up of adverse events will continue through the last day on study (including the follow-up, off study medication period of the study), until the Investigator and/or RTI International determine that the participant's condition is stable, or up to 30 days after the last dose of study drug, whichever is longer. RTI International may request that certain adverse events be followed until resolution.

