## **10. ADVERSE EVENTS**

Reports of adverse events will be collected during the trial, and the Research Monitor is required to review all unanticipated problems involving risk to volunteers or others, Serious Adverse Events (SAE) and all volunteer deaths associated with the protocol and provide an unbiased written report of the event to the USAMRMC Office of Research Protections (ORP) Human Research Protection Office (HRPO).

An adverse event (AE) is any untoward medical occurrence in a clinical investigation participant administered a medicinal product and which does not necessarily have a causal relationship with this treatment. An AE can therefore be any unfavorable and unintended sign, symptom, or disease temporally associated with the use of a medicinal product, whether or not considered related to the medicinal product. AEs may also include pre- or post-treatment complications that occur as a result of protocol-mandated procedures (e.g. invasive procedures such as venipuncture, biopsy, etc.). Pre-existing events, which increase in severity or change in nature during or as a consequence of use of a medicinal product in human clinical trials, will also be considered AEs.

An AE does not include:

- Medical or surgical procedures (e.g. surgery, endoscopy, tooth extraction, transfusion); the condition that leads to the procedure is an adverse event.
- Pre-existing diseases or conditions or laboratory abnormalities present or detected prior to the screening visit, that do not worsen.
- Situations where an untoward medical occurrence has not occurred (e.g. hospitalization for elective surgery, social and/or convenience admissions).
- Overdose of either study drug or concomitant medication without any signs or symptoms unless the participant is hospitalized for observation.

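### Adverse events must be recorded to the last study day, but no standard adverse event enquiry is scheduled, so non-suicidality events after week 2 appear to rely on spontaneous report

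*Protocol*

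**What the plan says.** **The duty to record.** In the Protocol Synopsis (Criteria for Evaluation), the whole safety entry is "adverse events". Protocol 7.2 asks for any AE "with an onset date after the screening visit up to the last day on study" to be entered on the CRF, and states that this includes the follow-up period. Protocol 7.6.1 adds: "Follow-up of adverse events will continue through the last day on study", or longer in some circumstances.

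**How events come to light.** Protocol 7.1 says that "reports of adverse events will be collected during the trial", and SAP 10 opens with the same statement: "Reports of adverse events will be collected during the trial". Protocol 7.3 has the investigator assess each AE. None of these sections says who asks the participant, when, or in what words.

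**Contact after the injections.** Protocol 6.3 states: "Following the intervention, the treating physician should have no further contact with the participant except as required for participant safety". Protocol 6.4 expects the week 4, 6 and 8 instruments, apart from the final CAPS-5, to be completed on participants' own devices. Protocol 6.4.4 says that in most cases the assessment runs through a web portal, and explains that "there will be no interaction between the participant and the RC at these times".

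**Analysis.** SAP 10 gives definitions and causality categories but specifies no AE table. SAP 8.2 has a general rule that data are summarised by treatment group, with counts and percentages for categorical measures.

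**The concern.** The plan sets a recording duty that runs to the end of follow-up, but describes no routine step by which a site would learn of most events once the participant has gone home after the second injection. A participant who develops a problem in week 3 and is treated elsewhere would enter the AE data only by thinking to tell someone on the study.

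Two things are at stake. First, unprompted reporting may miss non-serious and delayed events, so AE counts could be too low. Second, reporting could depend on what participants believe they received. Protocol 3.1 accepts that a successful block may be recognised by the participant, and Protocol 6.4.12 collects the participant's guess of arm at week 4. If people who believe they had the active procedure are more or less ready to link a symptom to the study, the comparison between arms could be distorted. Later analysis cannot recover events that were never elicited.

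**Working it through.** The plan states no figure on this point, so there is nothing to reproduce. The check sets the recording duty beside each scheduled contact, followed by simple day arithmetic.

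**Contacts after the first injection, and what each is described as asking**

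| Time | Contact and content | Described as general AE enquiry? |
|---|---|---|
| Weeks 0 and 2, after injection (Protocol 6.3) | Observation for complications, monitored recovery of 20 minutes or more, Horner's rating at 30 minutes, discharge advice | Immediate complications only |
| Week 2, before injection (6.3) | Nursing interim history, review of systems and vital signs; physician's targeted history and physical; PCL-5, PCL-C, K6, suicidality items | Could bring out events after the first injection; no stated link to the AE CRF |
| Week 4 (6.4.2 to 6.4.12) | Web: symptom scales, suicidality, alcohol, SF-12, pain, medications, perceived change, guess of arm | No |
| Week 6 | Web: PCL-5, PCL-C, suicidality, K6, perceived change | No |
| Week 8 | Web: as week 4 without the guess of arm; CAPS-5 by telephone (6.4.1) | No; the safety procedure described for the interview is the distressed-respondent protocol (6.2.2.4) |
| Between assessments | Reminder emails and calls (6.4, Appendices 19-1 and 19-2) | Content not available |
| Any positive answer on current suicidality | Automated alert, coordinator responds first (6.4.13) | Suicidality only |

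Table 1 has 11 rows, and none is for AEs. The pain scale, SF-12, medication list and perceived-change question might hint at a health problem, but none asks about a new event and none is described as leading to an AE form. The suicidality alert shows that the web system can route a safety answer to staff. It is not described as doing so for anything else.

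**Length of the period without a described enquiry**

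- Last scheduled in-person study visit: week 2 = 2 × 7 = day 14.
- Nominal final assessment: week 8 = 8 × 7 = day 56.
- Interval: 56 − 14 = 42 days; 42 / 56 = 75% of the time from week 0.
- End of the week 8 window, which closes 11 days after the due date (Protocol 6.4): 56 + 11 = day 67. Interval: 67 − 14 = 53 days; 53 / 67 = 79%.

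These are shares of calendar time, not of risk or of events. The documents give no AE rate over time and no reporting sensitivity, so the number of missed events cannot be calculated. No sample size or power figure is affected.

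**The case against.** The strongest reply is that Protocol 7.1 says this is not a safety study, and that neither document lists a safety objective. The block is described there as well studied. The severe complications named in Protocol 7.2 are largely tied to the procedure itself, and Protocol 6.3 expects local effects to last 6 to 18 hours. Observation after each injection and the week 2 review would therefore cover much of the risk. Serious events also have a 24-hour reporting route and Research Monitor review.

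Much of this stands, and it rules out several stronger readings:

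- **No coordinator contact in weeks 4 to 8.** A reader might infer this from Protocol 6.4.4. That sentence is qualified to most cases and concerns the moment of web completion. Reminder calls exist, the coordinator answers suicidality alerts, and the CAPS-5 at week 8 is live.
- **Nothing elicits AEs at all.** This fails for the first injection, because week 2 includes a history, a review of systems and an examination. It also fails for suicidality.
- **Three quarters of AEs go unasked.** The 75% treats each day as equally risky, which the documents do not support.
- **The SAP has no rule for reporting AEs by arm.** SAP 8.2 gives a general one. What is missing is an AE-specific table.
- **An AE question is shown to be absent from the trial.** Protocol section 6 refers to Appendix 1 for procedures. That appendix, Appendices 19-1 and 19-2 and the CRFs were not available, so a question there cannot be excluded.

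What the reply does not remove is the recording duty in Protocol 7.2, which applies whether or not the trial is called a safety study. The 24-hour clock in Protocol 7.6.1 starts only when the investigator knows of the event. The week 2 review cannot detect anything that follows the second injection.

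**Conclusion.** The point holds in a limited form. The available text contains no scheduled, standardised AE enquiry. After the week 2 visit, from day 14 to about day 56, capture of AEs other than suicidality appears to rest on spontaneous report. Non-serious and delayed events are the ones most likely to be missed. Reporting that differs by perceived arm is possible, but the documents do not demonstrate it. Neither effect can be sized.

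The conclusion assumes that the unavailable appendices and CRFs contain no AE prompt; if they do, the remedy is simply to cite it in the protocol. It also assumes that the reminder calls and the CAPS-5 interview follow their described purpose and do not routinely ask about health events. The CAPS-5 primary analysis is untouched. The consequence is for how AE rates may be read: as volunteered reports, not as solicited incidence.

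**What to change.** 1. Check Appendix 1, Appendices 19-1 and 19-2 and the CRFs for an AE prompt. If there is one, state in Protocol 6.3, 6.4 and Table 1 when, how and by whom AEs are elicited.
2. If there is none, add one fixed question to the existing computer assessments at weeks 2, 4, 6 and 8, worded identically in both arms: any new or worse health problem, or any medical care sought, since the last assessment. Route any yes to the coordinator for the AE CRF. Add the row to Table 1.
3. In SAP 10, add a table by arm of the number and percentage of participants with any AE, any related AE and any SAE, with solicited and spontaneous events shown separately.

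The cost is one item on forms already in use and one table. The downside is more minor AE forms and a higher reported AE rate. SAP Addendum 2 was written after unblinding, in answer to journal reviewers, so new questions can no longer help the data from this trial. The table and a plain statement of how AEs were ascertained can still be added.
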